# Statistical Analysis Plan (SAP) for Vertebral artery Ischaemia Stenting Trial (VIST)

# 1. SHORT DESCRIPTION OF PROJECT

Does vertebral artery stenting prevent recurrent stroke in symptomatic vertebral artery stenosis?

See VIST clinical study protocol Version 8.0 (10th June 2014) for details.

VIST is an international multicentre randomised controlled trial with the main aim to investigate the risks and benefits of vertebral angioplasty and stenting plus best medical treatment for symptomatic vertebral stenosis compared with best medical treatment alone. The efficacy is determined for the cohort as a whole and for extracranial and intracranial vertebral stenosis separately.

From an analytic point of view, we are treating VIST as a non-inferiority or equivalence trial, that is, a trial aimed to determine whether stenting is as good as best medical therapy alone in preventing recurrent stroke in patients with vertebral artery stenosis.

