In analyses of primary and secondary endpoint events at 3 months post-randomisation and during complete follow-up, follow-up will start immediately after randomisation. Follow-up will range from 1 year for the last recruited patients to about 7.5 years for first recruited patients. If the event numbers are sufficient, hazard ratios with 95% confidence intervals will be estimated by using Cox proportional hazards regression models, with patients censored at the time of first event of each type, death, last contact date, or the end of follow-up. The proportional hazards assumption for the treatment will be tested using Schoenfeld residuals. Kaplan-Meier survival analysis will be used to construct time-to-event curves, and the log-rank test will be used to evaluate whether there is a statistical significance difference in the cumulative risk of stroke between the two treatment groups.

We will also analyse short term outcomes to assess the operative risk. For this we have chosen a 30 day follow-up period but this may be adjusted before unblinding to results and analysis if we find stenting has not been carried out by 30 days in a significant number of individuals. For 30-days events, follow-up for each patient will start immediately after recruitment for patients allocated medical treatment alone and immediately after the stenting procedure for patients allocated stenting. If stenting was not performed in a patient allocated stenting, follow-up will begin directly after randomisation. The proportions of outcome events within 30-days of treatment will be compared with exact logistic regression to estimate odds ratios and 95% confidence intervals.

In additional analyses, provided that the event numbers are sufficient, we will adjust for centre and predefined risk factors (i.e., age, sex, body mass index and the vascular factors presented in Table 1). Hypothesis tests will be 2-sided using a significance level of 0.05. Statistical analysis will be performed using Stata (StataCorp, College Station, TX).

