#### 3.5. Sample size calculations

At trial initiation, we did power calculations using a power of 80% and two-sided significance level of 5%, and assuming that the risk of stroke in the medically treated arm would be 12% in year 1, 7% in years 2, and 5% in years 3 (i.e. 24% over a 3-year period). It was further assumed that the risk reduction in the stented arm would be 45% (including periprocedural rate). Based on these assumptions, the number of patients needed was estimated to be 490 (245 per arm). This number was increased by 10% to allow for stent failure, crossover, and loss to follow-up, thus giving a sample size of 540 patients. Because of early termination of the trial owing to low recruitment rate, the actual number of patients enrolled was 182.

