#### **FIGURE LEGENDS**

Figure 1. Flow of patients (see page 2)

Figure 2: Kaplan-Meier curves of cumulative probability of any stroke during follow-up, according to treatment group (intention-to-treat population)

Log-rank test is used to test the hypothesis that the cumulative incidence of stroke is the same in the two groups.

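### Section 1 declares a non-inferiority or equivalence trial, but the SAP sets no margin or confidence-limit rule and sizes and tests VIST for superiority, so its planned test cannot support the declared conclusion

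*SAP*

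**What the plan says.** **Declared aim.** SAP Section 1: "From an analytic point of view, we are treating VIST as a non-inferiority or equivalence trial", glossed as "a trial aimed to determine whether stenting is as good as best medical therapy alone in preventing recurrent stroke". The same section opens with a different question: "Does vertebral artery stenting prevent recurrent stroke in symptomatic vertebral artery stenosis".

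**Sizing.** SAP Section 3.5: "we did power calculations using a power of 80% and two-sided significance level of 5" per cent, with a control-arm stroke risk of 24% over three years. The only effect size given is a benefit: "It was further assumed that the risk reduction in the stented arm would be 45% (including periprocedural rate"). The result is 490 patients (245 per arm), raised to 540. Enrolment ended at 182.

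**Test.** SAP Section 3.3: "the log-rank test will be used to evaluate whether there is a statistical significance difference in the cumulative risk of stroke", and "Hypothesis tests will be 2-sided using a significance level of 0.05". The legend to Figure 2 states the null hypothesis: "Log-rank test is used to test the hypothesis that the cumulative incidence of stroke is the same in the two groups".

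**Estimates and analysis sets.** Section 3.3 and Table 3 plan hazard ratios with 95% confidence intervals. The main analysis is by intention to treat (ITT), with a per-protocol (PP) analysis as well. The SAP does not say how the two would be combined to reach a non-inferiority conclusion.

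**The concern.** Non-inferiority and equivalence are different hypotheses. Non-inferiority needs one margin on the unfavourable side; equivalence needs a bound on each side. In both, the conclusion comes from setting confidence limits against those bounds. The SAP names both designs, picks neither and supplies no bound, so the aim in Section 1 cannot be carried out.

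What it does supply is a test whose null hypothesis is equality. Failing to reject equality is not evidence of equality, least of all in a trial that reached about a third of its planned size (182/540 = 34%). At stake is how the primary result is interpreted. Section 1 promises an answer on whether stenting is as good, the planned test cannot give it, and the SAP has no safeguard against a null p-value being used in its place.

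**Working it through.** **Inputs.** From SAP Section 3.5: control risk 12% + 7% + 5% = 24% over three years; 45% reduction; two-sided 5%; 80% power; 490 before inflation; 182 enrolled. Assumed: 91 per arm (the plan was 1:1), the three-year risk as the event horizon, and proportional hazards. z(0.975) = 1.960 and z(0.80) = 0.842; their sum is 2.802 and its square 7.849.

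**1. Reproduce 490.** The SAP names no formula. Freedman's log-rank formula with HR 0.55:
- Events = 7.849 × [(1 + 0.55)/(1 − 0.55)]² = 7.849 × 11.864 = 93.1.
- Stented-arm risk = 1 − 0.76^0.55 = 0.140; mean risk = (0.240 + 0.140)/2 = 0.190.
- N = 93.1/0.190 = 490 (495 if events are first rounded up to 94).

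Other superiority formulas come close when the yearly risks are compounded to 22.3%: 484 (two proportions with continuity correction) and 500 (Schoenfeld). The stated size therefore follows from superiority inputs with no margin.

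**2. Power at 182 for the planned effect.**
- Events: 91 × 0.24 = 21.8 in the control arm. The stented arm has 91 × 0.132 = 12.0 (45% off the risk) or 91 × 0.140 = 12.7 (HR 0.55). The total is about 34.
- SE(log HR) = 2/√34 = 0.343; |ln 0.55| = 0.598.
- Power = Φ(0.598/0.343 − 1.96) = Φ(−0.22) = 0.41.
- Range: 20 events give 27% and 45 events give 52%. Two proportions at 91 per arm give 40% (24% vs 14%) to 46% (24% vs 13.2%). Reading the 45% as a risk ratio, so that HR = ln 0.868/ln 0.76 = 0.516, gives 49% at 34 events.

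**3. Precision at a true HR of 1.** Both arms now carry 24% risk, so the event count is not the one in step 2.
- Events = 182 × 0.24 = 43.7; SE = 2/√43.7 = 0.303.
- 95% CI around an observed HR of 1.0: exp(±1.96 × 0.303) = 0.55 to 1.81.
- HR margin with 80% power (one-sided 0.025): exp(2.802 × 0.303) = 2.33.
- Power at assumed margins, Φ(ln m/0.303 − 1.96): 11% at 1.25, 27% at 1.5, 63% at 2.0.

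**4. Non-significance when stenting is harmful.** Stented-arm risk = 1 − 0.76^HR, and events = 91 × (0.24 + that risk).

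| True HR | Stented risk | Events | P(p>0.05) |
|---|---|---|---|
| 1.5 | 33.7% | 52.5 | 69% |
| 1.75 | 38.1% | 56.5 | 44% |
| 2.0 | 42.2% | 60.3 | 23% |

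For HR 1.5: SE = 2/√52.5 = 0.276, and 1 − Φ(0.405/0.276 − 1.96) = 0.69. With the count held at about 44 events it is 73%.

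**The case against.** The best defence is that the label changes no planned computation. Hazard ratios with 95% confidence intervals are planned, and they would show the imprecision. Two-sided 5% is compatible with non-inferiority, because a two-sided 95% interval corresponds to a one-sided 2.5% test. Running ITT and PP analyses side by side is what a non-inferiority trial would normally want. All of this stands, so neither the sidedness nor the analysis sets are part of the fault. The fault is the missing margin, decision rule and choice of design, beside a test of equality.

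Could 490 be a non-inferiority size? A risk-difference margin of 10.8 points at 24% gives 7.849 × 2 × 0.24 × 0.76/0.108² = 245.5, or 246 per arm and 492 in all. But the SAP states no such margin and presents the 45% as an assumed risk reduction, so the match is coincidental.

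A reader might infer four stronger things that the document does not support:
- **That p>0.05 will be taken as proof that stenting is as good.** No section states that rule. The point is only that nothing rules it out.
- **That a null result is the likeliest outcome whatever the harm.** This holds at HR 1.5, but not at 1.75 or 2.0 under the assumptions used here. Even for the planned benefit it fails at the top of the event range, where power is 52%.
- **That it is too late for a credible margin.** Section 3.3 allows the 30-day window to be adjusted before unblinding, so the SAP presents itself as written before results were seen. The end of recruitment is not unblinding.
- **That Section 3.5 claims 80% power for 182 patients.** It dates that calculation to trial initiation and discloses the early stop.

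The protocol is not at hand and could contain a margin. The SAP cites none, and its own sizing and tests would still conflict with Section 1.

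**Conclusion.** Wrong as written. The aim declared in Section 1 cannot be answered by the analysis specified in Sections 3.3 and 3.5 and the Figure 2 legend. The contradiction is on the face of the SAP and depends on no assumption.

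The size of the interpretive risk does depend on assumptions: 91 per arm, 24% control risk and a three-year horizon. On those, a null result would be compatible with close to a halving or close to a doubling of stroke risk. Follow-up runs from 1 to about 7.5 years, so the true event count could be higher and the precision better. At 45 events, however, power for HR 0.55 is still only about one half.

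**What to change.** Before unblinding:

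1. Delete the non-inferiority/equivalence sentence in Section 1. State that VIST is analysed as a two-sided superiority trial by ITT, with PP as supportive.
2. Add that conclusions rest on the HR and its 95% confidence interval, and that p>0.05 will not be described as equivalence or as showing that stenting is as good as medical therapy.

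If the sponsor does intend non-inferiority, the SAP must instead name that one design, justify a margin, give the confidence-limit rule and define the roles of ITT and PP. It should also acknowledge that 182 patients give 80% power only for an HR margin of about 2.3.

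Optionally, note in Section 3.5, beside the historical 80%, that power at 182 patients for the planned effect is roughly 40-50%, with the assumptions behind it.

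The cost is a change of wording with no new data or analyses. The stated power looks less favourable, and under the superiority route the sponsor gives up an as-good-as claim.

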# 2. DATA

A summary of the participant assessments and data collection is described in the table below.

	Baseline Visit	Time of	1 month	6 months	1 year	Annual Telephone
	(Hospital Visit	Procedure*	(Hospital	(Telephone	(Hospital	Follow-up from Year 2
	1)	(Hospital Visit 2)	Visit 3)	Follow-up Call)	Visit 4)	until Trial End
Informed Consent	V					
Patient Diary	V					
Entry Form +	V					
Imaging Form	V				V	
Stenting Form		V				
Follow-up Forms‡			v	V	V	V
Cross-Over Form		V	v	V	V	V
Endpoint Form			v	v	v	V
Adverse Event Form		V	v	v	V	V
Death Report Form		V	V	V	V	V

\*If allocated angioplasty/stenting.

+Baseline data, including patient details, cerebral events (presenting and past events), risk factors, medication prior to trial entry, modified Rankin at time of randomisation, quality of life form completed, imaging prior to randomisation, and final screening prior to randomisation.

‡Follow-up forms include details on events since last follow-up, modified Rankin at time of follow-up, quality of life form completed, risk factors, medications at follow-up, and procedures performed since randomisation.

# 3. PLANNED STATISTICAL ANALYSES

#### 3.1. Flow diagram

See Figure 1 for a proposed detailed presentation of participant flow.

The number of participants randomised to each treatment arm, followed-up, and analysed will be presented with a CONSORT flow diagram.

# **3.2.** Descriptive statistics

See Table 1 below for a proposed presentation of the baseline characteristics.

Participants of each randomised treatment group will be described with regards to baseline demographic and clinical characteristics as recorded at the Baseline Visit. Categorical variables will be presented as numbers and proportions, and groups will be compared using  $\chi^2$  or Fisher's exact test. Continuous variables will be presented as means with standard deviations, and groups will be compared using *t* tests.

# 3.3. Comparison of treatment strategies

See Table 2 below for a proposed presentation of primary and secondary endpoints.

Main analyses will be performed on an intention-to-treat (ITT) basis, with inclusion of all randomised patients in the analysis according to the treatment group they were initially allocated. Analyses will also be done per-protocol (PP), including participants who met the inclusion criteria and received the assigned treatment. During trial monitoring is has become apparent that, for some cases, vertebral stenosis of at least 50% has not been confirmed on central imaging review.

The per-protocol analysis will include:

- 1. Patients with symptomatic vertebral stenosis from presumed atheromatous disease
- 2. Patients in whom central imaging review confirmed vertebral stenosis of ≥50%
- 3. Patients who received the allocated treatment

ITT and PP analyses will be performed for the primary and secondary endpoints, which are listed below. Not all secondary endpoints may be reported in the published article but the following analyses will be presented in the study plan;

Primary endpoint:

• Fatal and non-fatal stroke in any arterial territory during trial follow-up

Secondary endpoints:

- Fatal or non-fatal stroke in any arterial territory at 3 months post-randomisation
- Posterior circulation stroke (including periprocedural stroke) during follow-up
- Periprocedural stroke or death (within 30 days of procedure)
- Posterior circulation stroke and TIA during follow-up
- Any disabling stroke (defined by a Modified Rankin score ≥3) during follow-up
- Death of any cause during follow-up
- Restenosis (stenosis >50% in the treated artery) in treated artery during follow-up
- NHS and personal social services costs (UK patients only)\*
- Quality-adjusted life years\*
- Within-trial and long-run incremental cost-effectiveness\*

\*As specified in the protocol (pages 12-13).

The main analyses will be repeated for intracranial and extracranial strokes separately.

The intensity of medical treatment will be compared between the two groups over the first 30 days and over the full trial duration by assessing presence/absence and number of the following treatments: anti-platelets; statins; antihypertensives. Blood pressure measurements during follow-up in the two groups will be compared. Treatment of diabetes mellitus and current smoking will be recorded.

In analyses of primary and secondary endpoint events at 3 months post-randomisation and during complete follow-up, follow-up will start immediately after randomisation. Follow-up will range from 1 year for the last recruited patients to about 7.5 years for first recruited patients. If the event numbers are sufficient, hazard ratios with 95% confidence intervals will be estimated by using Cox proportional hazards regression models, with patients censored at the time of first event of each type, death, last contact date, or the end of follow-up. The proportional hazards assumption for the treatment will be tested using Schoenfeld residuals. Kaplan-Meier survival analysis will be used to construct time-to-event curves, and the log-rank test will be used to evaluate whether there is a statistical significance difference in the cumulative risk of stroke between the two treatment groups.

We will also analyse short term outcomes to assess the operative risk. For this we have chosen a 30 day follow-up period but this may be adjusted before unblinding to results and analysis if we find stenting has not been carried out by 30 days in a significant number of individuals. For 30-days events, follow-up for each patient will start immediately after recruitment for patients allocated medical treatment alone and immediately after the stenting procedure for patients allocated stenting. If stenting was not performed in a patient allocated stenting, follow-up will begin directly after randomisation. The proportions of outcome events within 30-days of treatment will be compared with exact logistic regression to estimate odds ratios and 95% confidence intervals.

In additional analyses, provided that the event numbers are sufficient, we will adjust for centre and predefined risk factors (i.e., age, sex, body mass index and the vascular factors presented in Table 1). Hypothesis tests will be 2-sided using a significance level of 0.05. Statistical analysis will be performed using Stata (StataCorp, College Station, TX).

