# Table 4. Serious adverse events within the first 30 days (intention-to-treat population)

CI, confidence interval; mRS, modified Rankin Scale; OR, odds ratio; TIA, transient ischemic attack.

ANALYSIS OF ANGIOGRAPHIC IMAGING DURING					
STENTING					
	Pre-Stenting	Immediate post-stenting			
Angiographic stenosis	? mean (SD)	? mean (SD)			
REPEAT NON-INVASIVE IMAGING AT 1 YEAR					
	At randomisation	At 1 year			
No. (%) with stenosis ≥50%					
Angioplasty/stenting					
Best medical therapy					
REPEAT NON-INVASIVE IMAGING AT 1 YEAR No. (%) with stenosis ≥50% Angioplasty/stenting Best medical therapy	At randomisation	At 1 year			

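### The per-protocol set conditions on receiving the allocated treatment while time runs from randomisation, which biases that comparison towards stenting; no as-randomised analysis of confirmed stenosis is planned

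*SAP*

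**What the plan says.** SAP section 3.3 makes ITT the main analysis: "Main analyses will be performed on an intention-to-treat (ITT) basis, with inclusion of all randomised patients in the analysis according to the treatment group" originally assigned. It then adds a PP analysis, "including participants who met the inclusion criteria and received the assigned treatment", and remarks that "for some cases, vertebral stenosis of at least 50% has not been confirmed on central imaging review". Three PP criteria follow:

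1. symptomatic stenosis presumed to be atheromatous;
2. "Patients in whom central imaging review confirmed vertebral stenosis of ≥50" per cent;
3. "Patients who received the allocated treatment".

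The scope is wide: "ITT and PP analyses will be performed for the primary and secondary endpoints, which are listed below".

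For events at 3 months and over complete follow-up, the same section says that "follow-up will start immediately after randomisation". It makes no exception for PP. Only the 30-day analysis starts stented patients at the procedure. Censoring is at first event, death, last contact or end of follow-up. The SAP plans no landmark analysis or time-dependent treatment term, and no as-randomised analysis restricted to criteria 1 and 2 alone.

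**The concern.** Criteria 1 and 2 describe the patient at entry, so restricting on them preserves the randomised comparison if they are read from entry data. Criterion 3 does not. To enter PP, a patient allocated stenting must survive to the procedure and remain fit for it. A stroke or death that prevents stenting removes both patient and event. Those who are stented bring waiting time from randomisation that is largely event-free by selection. No matching filter applies to early events in the medical arm.

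The SAP foresees these conditions. Section 3.3 allows that a significant number may not be stented by 30 days and has a rule for patients allocated stenting who never receive it. Section 3.5 inflates the sample size partly for crossover.

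Two features give PP more weight than a routine supplement. Section 1 treats the trial as non-inferiority or equivalence, a setting in which PP results are commonly read alongside ITT. Section 4 also places PP results next to ITT in the baseline and endpoint tables, or in a matching separate table.

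**Working it through.** **The plan's own figure.** Section 3.5 gives control risks of 12%, 7% and 5% in years 1 to 3, a 45% reduction, 80% power and two-sided 5% significance, leading to 490 patients. Applying the reduction to each year and compounding:

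- control: 1 − 0.88 × 0.93 × 0.95 = 0.2225
- stenting: 1 − 0.934 × 0.9615 × 0.9725 = 0.1267

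The pooled-variance two-proportion formula gives 245 per arm, 490 in total, so the figure reproduces. The same control risks are used below.

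**Set-up.** Assume no treatment effect, so both arms have the control risk. F(t) is the cumulative stroke risk at time t, and d is the delay from randomisation to stenting. Stenting-arm patients with a stroke before d are dropped from PP; time runs from randomisation.

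Assumptions not in the SAP:
- d is 7, 14, 30 or 60 days;
- 91 patients per arm (182 enrolled, split equally);
- the year-1 hazard is constant, or 50% or 70% of it falls in the first 90 days.

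Deaths before stenting are not modelled.

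**3-year hazard ratio.** The retained stenting patients are a fraction 1 − F(d) of their arm. The medical arm falls to the same fraction by day d, so the risk sets are nearly equal throughout, and

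null HR ≈ [F(3 y) − F(d)] / F(3 y), with F(3 y) = 0.2225.

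Example, constant hazard, d = 60: (0.2225 − 0.0208)/0.2225 = 0.91. Expected pre-stent strokes: 91 × 0.0208 = 1.9.

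| Year-1 hazard | | 7 d | 14 d | 30 d | 60 d |
|---|---|---|---|---|---|
| Constant | F(d) | 0.0024 | 0.0049 | 0.0105 | 0.0208 |
| | pre-stent strokes of 91 | 0.22 | 0.45 | 0.95 | 1.89 |
| | HR, formula | 0.99 | 0.98 | 0.95 | 0.91 |
| | HR, simulated Cox | 0.98 | 0.98 | 0.96 | 0.90 |
| 50% in 90 days | F(d) | 0.0050 | 0.0099 | 0.0211 | 0.0417 |
| | pre-stent strokes of 91 | 0.45 | 0.90 | 1.92 | 3.80 |
| | HR, formula | 0.98 | 0.96 | 0.91 | 0.81 |
| | HR, simulated Cox | 0.98 | 0.95 | 0.91 | 0.81 |
| 70% in 90 days | F(d) | 0.0069 | 0.0138 | 0.0294 | 0.0579 |
| | pre-stent strokes of 91 | 0.63 | 1.26 | 2.67 | 5.27 |
| | HR, formula | 0.97 | 0.94 | 0.87 | 0.74 |
| | HR, simulated Cox | 0.97 | 0.94 | 0.86 | 0.74 |

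The simulation used 400,000 patients per arm and agrees with the formula to about 0.01. If only half of the patients with a pre-stent stroke are dropped, the simulated range is 0.99 to 0.87.

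**3-month risk ratio.** Null RR = {[F(90) − F(d)] / [1 − F(d)]} / F(90). With a constant hazard F(90) = 0.0310, and at d = 30 this is (0.0205/0.9895)/0.0310 = 0.67. For 7, 14, 30 and 60 days the results are 0.92, 0.85, 0.67 and 0.34. They barely change with hazard shape, because each shape is flat within the first 90 days. If half are dropped, F(d) is replaced by F(d)/2 in both brackets: at d = 60, (0.0206/0.9896)/0.0310 = 0.67.

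**Without criterion 3.** Restricting on criteria 1 and 2 at baseline and analysing as allocated removes no one because of later events, so the null HR is 1.00 by construction.

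**The case against.** **ITT is the main analysis and is untouched.** This stands, and it limits the point to a supporting analysis. It does not remove the point, given the section 1 framing and the side-by-side tables.

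**Imprecision swamps the bias.** About 20 strokes per arm are expected by 3 years (91 × 0.2225). The standard error of log HR is then about √(2/20) = 0.32, giving an interval of roughly 0.54 to 1.86 around 1.0. Every 3-year shift above lies inside it, and with prompt stenting the shift is small. This is fair as to size. But the bias from dropped pre-procedure events runs one way and can be avoided.

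**Treatment received was always part of PP.** This also stands. A reader might infer that a clean confirmed-stenosis analysis was intended and then spoiled by criterion 3. The text does not say so: receipt of treatment is in the opening definition, before the remark on unconfirmed stenosis. What can be said is that no as-randomised analysis addresses that remark.

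**Crossover.** A reader might infer that medical-arm patients stented after a recurrent event are also removed, which would push the HR the other way. The SAP never says this. Such a patient may well count as having received the allocated treatment. The handling is undefined, so no figure can be attached to it.

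**Imaging.** A reader might suspect that confirmation differs by arm, because the imaging table in section 4 has a procedural row ("Angiographic stenosis") that exists only for stented patients. Nothing links that row to PP eligibility. Section 2 lists pre-randomisation imaging as baseline data, and the same table reports stenosis at randomisation for both arms. A difference by arm is not supported.

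**Conclusion.** The point holds for the PP analyses of the 3-month and full follow-up endpoints. Conditioning on a post-randomisation event with time counted from randomisation favours stenting. Under no true effect and delays of 7 to 60 days, the 3-year HR is about 0.98 to 0.90 with a constant year-1 hazard and reaches about 0.74 only with a high early hazard and a long delay. The 3-month endpoint, a named secondary, is much more exposed, at about 0.92 to 0.34.

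These are upper sizes in one respect: they assume that every stroke before the procedure prevents stenting. Delay, hazard shape and equal arms are assumptions. The direction depends only on some pre-procedure events preventing stenting. The 30-day analysis does not carry the waiting-time credit.

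**What to change.** 1. Add a confirmed-stenosis analysis: all randomised patients meeting criteria 1 and 2 on central review of pre-randomisation imaging, analysed as randomised. Report it beside ITT for the primary and secondary endpoints.
2. Keep the treatment-received PP set, but label it a sensitivity analysis. Count strokes and deaths before the procedure in the stenting arm, or use a landmark or time-dependent treatment approach.
3. Define what counts as receiving the allocated treatment, and state how medical-arm patients stented later are analysed.

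PP need not be abandoned. Simple censoring at departure from allocated treatment should not be required, since without weighting it can itself be related to outcome.

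Cost: SAP wording and one extra analysis set, using the imaging, stenting and cross-over forms listed in section 2. The price is a treatment-received estimate that may be less favourable to stenting and less pure as a contrast of treatments actually given.

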# the whole study follow-up

	Best medical treatment group (n = xx)		Angioplasty/stenting group (n = xx)		
	First 30 days	Whole follow-up a	First 30 days	Whole follow-up a	
Antiplatelet medication					
Aspirin alone					
Clopidogrel alone					
Aspirin and clopidogrel					
Other					
Oral anticoagulants					
Statin therapy					
Antihypertensive medication					
Blood pressure b					
Systolic (mmHg)					
Diastolic (mmHg)					
Treated diabetes mellitus					
Non-insulin dependent					
Insulin dependent					
Current smoking					
a Where treatments ch	anged during follo	w-up the treatment give	n for the majority	of follow-up is	

recorded.

b Blood pressure measurements were only recorded at clinic follow-ups at 3 months and 1 year.

Table 3. Primary and secondary endpoint events during follow-upa (intention-to-treat population) (per-protocol data will be presented in columns to the right or in a separate similar table)

	No. (%) of patients/person-months			
	Best medical treatment	Angioplasty/stenting	HR (95% CI)	P value
	group (n = xx)	group (n = xx)		
Primary endpoint				
Fatal or non-fatal stroke in any arterial territory b				
Extracranial vertebral artery target stenosis				
Intracranial vertebral artery target stenosis				
Secondary endpoints				
Fatal or non-fatal stroke in any arterial territory b at 3 months				
Posterior circulation stroke b				
Periprocedural stroke or death				
Posterior circulation stroke or TIA				
Death from any cause				
CI, confidence interval; HR, hazard ratio; mRS, modified Rankin S	cale; TIA, transient ischemic	attack.		

a Complete follow-up (≥1 year) if not otherwise indicated.

b Including periprocedural (30 days post-procedure) stroke.

	No. (%) of			
	Best medical treatment	Angioplasty/stenting	OR (95% CI)	P value
	group (n = xx)	group (n = xx)		
Cerebrovascular event				
Fatal or non-fatal stroke				
Posterior circulation stroke				
Extracranial				
Intracranial				
Posterior circulation stroke or TIA				
Any disabling stroke (mRS score ≥3)				
Major operation related SAEs				
Death from any cause				

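### Periprocedural stroke or death is given an HR that conflicts with the SAP's own 30-day rule, operation-related SAEs are given an uninformative OR, and no analysis gives the operative risk among everyone who had a procedure

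*SAP*

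**What the plan says.** **Endpoint and analysis sets (section 3.3).** The secondary endpoint is "Periprocedural stroke or death (within 30 days of procedure"). The section adds: "ITT and PP analyses will be performed for the primary and secondary endpoints, which are listed below". ITT is defined "with inclusion of all randomised patients in the analysis according to the treatment group they were initially allocated". One of the three PP conditions is "Patients who received the allocated treatment"; another is stenosis of at least 50% confirmed on central imaging review.

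**Clocks and methods (section 3.3).** The survival analyses have one start: "In analyses of primary and secondary endpoint events at 3 months post-randomisation and during complete follow-up, follow-up will start immediately after randomisation". Cox HRs are to be estimated if there are enough events. A separate paragraph, whose stated aim is to assess operative risk, sets a 30-day period. It runs from recruitment in the medical arm, from the procedure in the stenting arm, and from randomisation for patients allocated stenting who are not stented. Proportions are compared by exact logistic regression, giving an OR with 95% CI.

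**Table shells (section 4).** Table 3 has a row "Periprocedural stroke or death" with columns for both arms, HR and P value, and no footnote of its own. Table 4, headed as an ITT table for the first 30 days, has a row "Major operation related SAEs" with columns for both arms, OR and P value.

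**Crossover.** In section 2 the procedure visit carries the footnote "If allocated angioplasty/stenting", and a Cross-Over Form is scheduled at the procedure and at each follow-up. Section 3.5 names crossover among the reasons for the 10% increase in sample size. No rule says how a procedure in a medical-arm patient is to be reported.

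**The concern.** Procedural harm is what has to be weighed against any benefit of stenting, and the SAP sets out to measure it. Three things stand in the way.

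- The Table 3 row and the 30-day paragraph call for different effect measures and different starting points for the same endpoint. Two analysts could fill the row differently and each claim to have followed the plan.
- The operation-related row in Table 4 tests a difference that exists because one arm was not assigned an operation. Its OR and P value say almost nothing about treatment.
- The figure a clinician would look for, the risk among patients who had the procedure, comes out of none of the planned analyses.

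**Working it through.** The SAP gives no figure for this point, so there is nothing to reproduce; the sample-size figures in section 3.5 are not affected. The check is to set the rules side by side and then illustrate their size.

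**1. Table 3 row against the 30-day paragraph**

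| | Table 3 row | 30-day paragraph, section 3.3 |
|---|---|---|
| Measure | HR, P value | exact-logistic OR, 95% CI |
| Start, medical arm | randomisation, if Cox | recruitment |
| Start, stenting arm | randomisation, if Cox | procedure (randomisation if not stented) |

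The Cox rule covers events at 3 months and during complete follow-up. A 30-day post-procedure event is neither, so the text points to the OR and the table to the HR.

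**2. A test case: medical-arm patient stented at month 10, with a stroke during the procedure**

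- Table 3 row, read by the endpoint's definition with a Cox clock: a medical-arm event.
- Table 3 row, read under the 30-day paragraph: outside the window, not counted.
- Table 4: outside the window, not counted.
- PP: patient excluded, not having kept to the allocated treatment.
- Primary ITT endpoint: counted in the medical arm, as it should be.

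The text does not settle which reading of the Table 3 row applies.

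**3. Who is in the operative-risk denominator**

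| Analysis | Never-stented, allocated stenting | Medical-arm crossovers | Stented, stenosis of at least 50% not confirmed |
|---|---|---|---|
| ITT, 30 days | kept | in medical arm, window from recruitment | kept |
| PP | removed | removed | removed |
| All patients with a procedure (not planned) | removed | kept | kept |

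**4. Size of the denominator effect (illustration)**

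Input from section 3.5: 182 enrolled. Assumptions: equal arms, 182/2 = 91; five procedural events, all in stented patients; 0%, 20% or 33% of the stenting arm never stented. Clopper-Pearson 95% limits for x events in n: lower = Beta quantile 0.025 (x, n − x + 1); upper = Beta quantile 0.975 (x + 1, n − x).

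| Never stented | Number stented | Risk | 95% CI |
|---|---|---|---|
| 0% | 91 | 5/91 = 5.5% | 1.8 to 12.4 |
| 20% | 91 × 0.80 ≈ 73 | 5/73 = 6.8% | 2.3 to 15.3 |
| 33% | 91 × 0.67 ≈ 61 | 5/61 = 8.2% | 2.7 to 18.1 |

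**5. What the operation-related OR would show (illustration)**

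Assumptions: 91 per arm and the event counts shown. Conditional maximum-likelihood OR with exact 95% CI; two-sided Fisher P.

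| Stenting v medical | OR (95% CI) | P |
|---|---|---|
| 3 v 0 | infinite (0.42 to infinity) | 0.25 |
| 5 v 0 | infinite (0.94 to infinity) | 0.059 |
| 8 v 0 | infinite (1.80 to infinity) | 0.007 |
| 3 v 1 | 3.1 (0.24 to 163) | 0.62 |
| 5 v 1 | 5.2 (0.56 to 250) | 0.21 |
| 8 v 1 | 8.6 (1.1 to 389) | 0.034 |

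An exact interval exists with a zero cell, but without crossover that zero follows from the design. One operation-related event in a medical-arm patient, which under the Table 4 clock would need a crossover soon after recruitment, moves the estimate a long way.

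**The case against.** A reader might go further and infer that the comparison of periprocedural stroke or death is undefined, with a medical-arm count of zero by construction and any small P value therefore empty. The SAP does not support that. Its 30-day paragraph gives the medical arm a window from recruitment and a stated method, and a medical-arm patient can have a stroke or die in that window without crossing over. The structural zero belongs to the operation-related row only. The other Table 4 rows (stroke, TIA, disabling stroke, death) can occur in either arm and are not in question.

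Other defences also have force:

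- Keeping never-stented patients in the stenting arm is the declared ITT rule, with a stated start date, and PP removes them. The dilution in step 4 is therefore an ITT matter. PP does not replace the missing analysis, because it also removes crossovers and patients without confirmed stenosis.
- Counting a crossover's stroke in the allocated arm is proper ITT, and the stroke still appears in the primary endpoint. It is not lost from the trial, only from its account of procedural harm.
- The tables are proposed shells with shared column headings, and HRs depend on event numbers. That may leave the Table 3 cell empty, but it does not say what the row means.
- SAE definitions are left to the protocol, which is not at hand. As worded, however, the row requires an operation.

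**Conclusion.** The point holds in three parts. The Table 3 row conflicts with the 30-day rule in section 3.3 on effect measure and clock. The OR and P value for operation-related SAEs are uninformative. No planned analysis estimates the risk among all patients who had a procedure, although the SAP says it will assess operative risk.

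These conclusions rest on the text alone. Their size cannot be read from it: arm sizes, event counts, the fraction never stented and the crossover rate are not given. Under the assumptions shown, the ITT figure would be 5.5% against 8.2% among those stented if a third of the arm had no procedure, with wide and overlapping intervals. If nearly all were stented and few crossed over, the third part would matter little; the first two would remain. The primary endpoint analysis is untouched.

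**What to change.** 1. **Table 4.** Remove the OR and P value from "Major operation related SAEs" and report the row descriptively.
2. **Operative risk.** Report periprocedural stroke or death and operation-related SAEs as n/N with exact 95% CI among all patients in whom a procedure was started, medical-arm crossovers included. Count from the start of that patient's procedure and show the result by randomised arm as well as overall. The Stenting and Cross-Over Forms are the natural sources.
3. **Table 3.** Remove the HR from "Periprocedural stroke or death". Keep the between-arm comparison of 30-day stroke or death set out in section 3.3, as an exact OR under its own label, with the arm-specific clocks in a footnote.
4. **Crossover.** State that strokes after crossover stay in the allocated arm for the primary ITT endpoint.

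The cost is SAP wording and table shells. The procedural rows lose a between-arm P value, and the reported operative risk may look less favourable than the ITT figure.
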